## **9. Adverse event reporting**

In the case of a reportable event, the Principal Investigator will submit the form "Reportable Protocol Event Form for VA sites" along with supporting documentation and to the VA Science Information Office. The SIO will then route the report to the Emory IRB. The Emory IRB will be notified within five days of any adverse event occurring.

## **10. Data Security Plan**

Information about subjects, including all research records created, will be held strictly confidential. Study files will be kept in a locked filing cabinet in the private office of the Principal Investigator at the Atlanta VA Medical Center (Room 12C-118). A study number rather than the subject's name will be used on study records whenever possible. The data collected with special software on the study laptops during the word learning tasks will be de-identified (subject number, visit number). The data will be exported to Excel spreadsheets and transferred from the password-protected laptop to password-protected files on the secure VA network using a VA-issued USB drive. Audio-

recordings will also be stored on the secure VA network in password-protected files. Blood samples will be stored in a de-identified manner. Collection tubes will be labeled with subject number, visit number and draw number. Samples may be temporarily stored at Emory University in the locked office of [name] (TEC B5601) while undergoing analyses. We will not use subjects' names or other identifying information when the study is presented or when the results are published. All research records and/or identifiers will be destroyed in accordance with the VA record retention schedule.

Official Study Title:

Acute Exercise Effects on Word Learning in Aging and Stroke-induced Aphasia

NCT# 03370471

Document Date: 09/16/19

Statistical Analysis Plan

The following analyses apply to data from healthy adult participants who completed the study:

Primary Outcome

Aim 1. We will use a mixed effects model approach to fit repeated measures ANOVAs to word recall scores obtained at three time points: 1) after learning (acquisition), 2) immediately before exercise or stretching on two days (consolidation), and one week after the final learning session (long-term recall).

Secondary Outcome

Aim 2. We will use a mixed effects model approach to fit repeated measures ANOVA to serum BDNF concentration levels (pg/mL) obtained at four time points: 1) before exercise or stretching, 2) immediately after exercise or stretching, 3) immediately after learning, and 4) 15 minutes after learning.

Post-hoc Analysis:

We will use a mixed effects model approach to fit repeated measures ANOVAs to word recognition scores obtained at three time points: 1) after learning (acquisition), 2) immediately before exercise or stretching on two days (consolidation), and one week after the final learning session (long-term recall).

The following analyses apply to data from participants with aphasia who completed the study:

Primary Outcome

Aim 1. We will calculate gains for word recall at three time points: 1) after learning (acquisition), 2) immediately before exercise or stretching on two days (consolidation), and one week after the final learning session (long-term recall).

Secondary Outcome

Aim 2. We calculate means of serum BDNF concentration level (pg/mL) obtained at four time points: 1) before exercise or stretching, 2) immediately after exercise or stretching, 3) immediately after learning, and 4) 15 minutes after learning.

Post-hoc Analysis:

We will calculate gain scores at three time points: 1) after learning (acquisition), 2) immediately before exercise or stretching on two days (consolidation), and one week after the final learning session (long-term recall).

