### 2. Abstract

**Objective:** Difficulty retrieving words, one of the most common language complaints in healthy older adults and those with mild cognitive impairment (MCI) stroke-induced language disorders (i.e., aphasia), can have a negative impact on communicative function. Consistent with studies in young adults, our pilot study in healthy older adults, demonstrates that acute exercise may improve word learning; however, more research is needed to optimize learning paradigms for healthy older adults and those with MCI and aphasia and to investigate the factors that contribute to exercise-induced improvements in learning in these populations. The objectives of this research are to: 1) identify an optimal novel word learning paradigm; 2) determine the acute effects of exercise (compared to stretching) on word learning; 3) investigate the influence of timing of exercise (exercise before vs. after learning); 4) investigate the influence of high vs. low working memory ability on exercise-enhanced word learning; and 5) investigate the neurophysiological correlates of exercise-enhanced word learning.

**Research Plan:** Word learning performance will be compared in up to four conditions (before exercise, after exercise, before stretching, after stretching). Performance of individuals with high vs. low working memory will be compared and peripheral levels of brain-derived neurotrophic factor (BDNF) and dopamine will be measured to investigate correlates of immediate and one-week retention of learned words.

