**Methods:** We will compare word learning in up to four conditions using a within-subjects crossover design. Individuals aged 65-89 years (healthy older adults and MCI) and 35-89 years (individuals with aphasia) who meet the eligibility criteria will be offered enrollment. In the exercise conditions, participants will engage in 30 minutes of moderate-intensity cycling (with a warm-up/cool-down) before or after word learning. In the stretching conditions, participants will engage in upper- and lower-limb stretching for 30 minutes before or after word learning. In the word learning task, participants will be asked to learn novel words ("flark") for a familiar object ("cup") and will engage in tests of recall and recognition. Each condition will last two weeks. In week 1, training /testing will take place on Monday, Wednesday and Friday of week 1 to measure immediate retention. In week 2, testing will take place on Friday to measure one-week retention. To measure serum levels of BDNF and dopamine, blood samples will be taken at baseline (every 15 minutes for one hour) and in the two training conditions when exercise/stretching occurs before word learning (immediately before exercise/stretching, immediately after exercise/stretching, immediately after word learning, and 15 minutes after word learning).

**Clinical Relevance:** The aging population of the US is expected to more than double by 2060, and a similar trajectory is expected within our aging veteran population.

Additionally, stroke affects 795,000 individuals per year, and up to 30% are left with chronic disability including language impairment. MCI can also have an impact across all cognitive domains, including language and memory (Arnaiz & Almkvist, 2003). The declines in communicative function that are present in healthy older adults and those with aphasia often result in reduced independence and psychosocial well-being, and they may contribute to poorer health outcomes. Investigating an exercise-based approach to improving word retrieval is clinically relevant and has the potential to have a significant impact on the functioning and well-being of thousands of aging veterans.

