#### **6. Overview of Design/Methods**

The study will enroll up to 100 healthy older adults and up to 50 older adults with MCI and stroke-induced aphasia. A crossover design will be used to compare two novel word learning paradigms and/or the additive effect of moderate-intensity exercise vs. stretching on novel word learning.

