A Dell laptop computer running EPrime 2.0 software and paired with a response box will be used to standardize stimuli presentation in the learning task and record the speed and accuracy of responses to the word recall and recognition tasks. Familiar objects will be paired with two-syllable nonwords that are 5-6 letters in length and phonologically plausible in the English language. Sets of stimuli will be balanced on the frequency and familiarity. The order of stimuli sets will be counterbalanced across subjects and conditions. During the word learning task, familiar objects will be randomly presented along with the target nonword, which will also be heard through headphones. Following the learning task, subjects will be administered a recognition task and a cued recall task. Verbal responses will be audio-recorded for scoring and reliability assessment. The number of stimuli, duration and number of exposures to stimuli, and feedback during testing will be manipulated to identify the optimal learning paradigm for investigation of acute exercise effects on word recall (Objective 1).

Exercise/Stretching:

- a) Exercise: Subjects will engage in supervised moderate-intensity cycling for 30 minutes with a warm-up and cool-down. They will be asked to reach and maintain their individual physiological training target (i.e., heart rate at which 50-75% of maximal oxygen uptake would be achieved as predicted by sub-maximal test administered during the baseline assessment).
- b) Stretching: Participants will participate in an upper- and lower-extremity stretching program for 30 minutes. The stretching program will provide the opportunity for 30 minutes of interaction without increasing heart rate.

Exercise and/or stretching will be paired with a novel word learning paradigm to determine the effect of moderate-intensity aerobic exercise (compared to a stretching control) on word recall (Objective 2). The exercise/stretching will be administered before and/or after word learning to better understand how acute exercise effects vary as a function of timing (Objective 3a).

Subjects will be asked to avoid any exercise that is not part of the study on training days and to avoid exercise before testing on the testing only days. No other restrictions will be placed on subjects regarding their exercise routines.

Mood and arousal measures:

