## 7. Patient Evaluation and Data Collection Timeline

Study Visit	Activity			# of hours
Pre Training				
Assessment I	· Consenting			2
	· Screening Tests			
	· Study Tests			
Assessment II + Blood draw (if applicable)	· Study Tests			2
	· Blood sample taken every 15 minutes for 1 hour			
Assessment III	· Study Tests			2
Training Conditions (in random order)				
Exercise + Word Learning + Blood draw** (if applicable)	M	W	F	**Before exercise, after exercise, after word learning, 15 min after word learning
	test/train/test	test/train/test	test/train/test	
			test	
	One week break			
Stretching + Word Learning + Blood draw** (if applicable)	M	W	F	**Before stretching, after stretching, after word learning, 15 min after word learning
	test/train/test	test/train/test	test/train/test	
			test	
	One week break			

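### On its plain reading, the SAP limits every healthy-adult analysis to an undefined completer set known only after randomisation, and drops partial records that the planned mixed model could use

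*SAP*

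**What the plan says.** The healthy-adult part of the SAP begins "The following analyses apply to data from healthy adult participants who completed the study" and then lists the primary (recall), secondary (BDNF) and post-hoc (recognition) analyses, all as repeated-measures ANOVAs fitted by a mixed effects model. The aphasia part begins "The following analyses apply to data from participants with aphasia who completed the study" and plans only gains and means.

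Neither document says what completing means. Neither names an all-randomised or all-available set, a missing-data rule or a sensitivity analysis.

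The schedule does not settle the meaning:

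- The table in Protocol section 7 shows two conditions, exercise and stretching, under the label "Training Conditions (in random order".
- The Abstract says "Word learning performance will be compared in up to four conditions".
- Section 6 describes a crossover to "compare two novel word learning paradigms and/or the additive effect of moderate-intensity exercise vs. stretching on novel word learning", and later says "The exercise/stretching will be administered before and/or after word learning".
- Each condition has four visits. Those of the first week "will take place on Monday, Wednesday and Friday of week 1 to measure immediate retention", and the fourth follows: "In week 2, testing will take place on Friday to measure one-week retention".
- Under Blood draws, section 6 says that only some subjects give blood.

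**The concern.** Whether someone finishes is known only after the order of conditions has been assigned, and it may depend on how that person fared in the first condition. A set chosen on that basis no longer has the full protection of random order. The SAP also picks a model that tolerates incomplete records and then, as worded, removes the people who have them.

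Three things are at stake: precision on the primary outcome, possible bias in the exercise-minus-stretching contrast, and reproducibility. Two analysts could form different primary sets from the same wording, and could do so after seeing data.

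**Working it through.** **Inputs.** From the documents: two conditions in random order with four visits each (Protocol Abstract and section 7), and at most 100 healthy adults (section 8). The SAP uses 1 or 3 recall scores after learning, 2 before exercise or stretching, and 1 at one week, so 4 to 6 per condition. The documents give no dropout rate, SD, correlation, effect size or sample-size calculation, so there is no plan figure to reproduce.

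Assumed: unit-variance scores, correlation 0.7 within a condition (range 0.6 to 0.8) and 0.5 between conditions (range 0.3 to 0.7 for bias). The hand calculations use three scores per condition, one per time point.

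**1. What completing could mean.** (a) Not withdrawn, with missed visits allowed. (b) Both conditions in the section 7 table. (c) Every visit: 2 × 4 = 8. (d) All of up to four conditions: 4 × 4 = 16 visits. Under (b), a person who leaves after the first condition loses all 4 to 6 recall scores.

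**2. Precision under (b).** Let a fraction *d* leave after the first condition, unrelated to score and equally in both orders. With 100 adults and *d* = 10/20/30%, 90/80/70 remain.

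- *Average effect.* The variance of a condition mean is v = 0.7 + 0.3/3 = 0.8. A completer's difference has variance 2(0.8 − 0.5) = 0.6. A one-condition record adds information 1/(4v) = 1/3.2. The completer-to-all-data variance ratio is 1 + [d/(1−d)] × 0.6/3.2 = 1.021/1.047/1.080.
- *One-week effect.* The completer variance of 1.0 splits into 0.6 from the average and 0.4 from contrasts between time points. For the contrasts the factor is 1 + [d/(1−d)] × 0.5. At 10% the ratio is 1/(0.6/1.0208 + 0.4/1.0556) = 1.034; at 20% and 30% it is 1.077 and 1.130.
- *Range* over within-condition correlations and 3, 4 or 6 scores: average effect 1.017–1.024/1.038–1.053/1.065–1.091; one-week effect 1.032–1.041/1.071–1.092/1.121–1.156.
- *Interval width:* √1.017 = 1.008 to √1.156 = 1.075, so about 1 to 8% wider.

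**3. Stricter readings.** If each visit is missed independently with probability 1/2/5%, all 8 are attended by 0.99⁸/0.98⁸/0.95⁸ = 92/85/66%, and completer variance rises 7–8/15–17/43–50% (interval about 4/7–8/20–22% wider). Under (d), with 10/20/30% leaving after the third condition, variance rises 8/17/29–30% (interval about 4/8/14% wider). Under (a), a missed visit costs nothing.

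**4. Bias when dropout depends on the observed first-condition score (true effect zero).** Let δE and δS be the rise in mean first-condition score among those who stay, in the exercise-first and stretching-first orders. Their second-condition mean rises by rδ, with r = 0.5/0.8 = 0.625. Averaging the exercise-minus-stretching difference over the two orders gives

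bias = (1 − r)(δE − δS)/2.

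With low scorers leaving on a logistic curve (slope 1.5 per SD of the condition mean), δ = 0.058/0.109/0.157/0.203/0.292 at 5/10/15/20/30% dropout.

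| Dropout, exercise-first v stretching-first | Bias (SD) |
|---|---|
| 10% v 5% | 0.375 × 0.051/2 = 0.010 |
| 15% v 5% | 0.375 × 0.099/2 = 0.019 |
| 30% v 5% | 0.375 × 0.234/2 = 0.044 |
| 20% v 20%, same relation | 0 |
| 20% v 20%, score-related in exercise-first only | 0.375 × 0.203/2 = 0.038 |
| 20% v 20%, opposite relations | 0.375 × 0.406/2 = 0.076 |

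Reversing the rates reverses the sign. Over the assumed correlations, 10% v 5% gives 0.01 to 0.02, 15% v 5% gives 0.01 to 0.03, and 30% v 5% gives 0.02 to 0.08. Simulation with 2,000,000 participants per scenario agreed with the first four rows (0.008, 0.018, 0.043, 0.001), and an all-data model stayed within about 0.002 SD. Simulated completer type I error at n = 40 and 100 was 4.8–5.3%, 4.8–6.0% and 5.8–8.5% in the first three rows (5,000 runs each).

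**5. Dropout that depends on unobserved scores.** Suppose 20% leave in each order because of the exercise-condition score, which in stretching-first has not yet been seen. Completers are then biased by (1 − r)δ = 0.375 × 0.203 = 0.076 SD (simulated 0.075) and the all-data model by 0.058. Across correlations these are 0.04–0.14 v 0.04–0.08, so the all-data model removes only 11 to 39%.

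**The case against.** The best defence is the design. In a two-condition crossover every completer supplies both conditions, so a one-condition record adds little and bias cancels when dropout works the same way in both orders. At 15% v 5% the type I error is at most 6.0%. The wording may also be only a loose description of the data. All of this stands as a limit on size, but nothing in the documents says that the wording is loose.

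A reader might infer three stronger points, which the documents do not support:

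- *One missed visit, or fewer than four conditions, excludes a person.* Four is a ceiling and section 7 shows two. The SAP's BDNF sequence fits activity before learning, and a mixed model sits poorly with a no-missed-visit rule. These readings are possible, not established. Whether all participants share one schedule is a separate ambiguity.
- *The primary result will be materially biased.* No dropout rate or imbalance is given, and the larger figures need heavy, unequal or differently driven loss. The opposite inference, that equal rates guarantee no bias, also fails, as the last two table rows show.
- *The completer rule invalidates the model's standard errors.* The all-data figures assume clustering both within participant and within condition. Choosing that covariance matters even with no dropout, so it is a separate model-specification point.

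**Conclusion.** The point holds as a defect in the analysis set that is cheap to repair. The SAP states a rule, leaves its key word undefined, and on the plain reading discards usable healthy-adult data after randomisation.

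On the only schedule shown, the precision cost is modest. Bias from dropout on observed scores needs a difference between orders in its rate or in its relation to score. It is 0.01 to 0.03 SD at modest imbalance, and about 0.04 SD in the heavier or one-sided cases at the central correlations. An all-data model removes that bias, but only part of any bias from dropout on unobserved scores.

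Every size rests on assumed rates and correlations, so the actual loss and its direction are unknown. In the aphasia group, where no model is planned, the issue is only which participants are summarised.

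**What to change.** For healthy adults, make the primary set all randomised participants with at least one post-randomisation value of the outcome being analysed. Analyse all available visits, by the condition assigned in each period, in the mixed model already planned. The entry rule should be specific to recall, recognition or BDNF, because only some participants give blood.

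Define completion: how many conditions, and whether a missed visit counts against it. Keep the completer analysis as a sensitivity analysis, and report withdrawals with reasons by condition and order. For aphasia, state who is summarised and give the number contributing at each time point and condition.

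The cost is a short SAP paragraph, one extra model run per outcome and a withdrawal table, with no new data. The downside is slightly more analysis work and reliance on missing at random, which the SAP should state.

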### **3. Objectives/Hypothesis/Research Questions**

- 1) To identify an optimal novel word learning paradigm for investigation of acute exercise effects on word recall
- 2) To determine the effect of moderate-intensity aerobic exercise (compared to a stretching control) on word learning
- 3) To investigate factors known to modulate acute exercise effects such as:
  - a. Timing of exercise (exercise before vs. after learning)
  - b. Individual differences (high vs. low working memory ability)
- 4) To investigate the neurophysiological correlates of exercise-enhanced word learning

*Research Question 1:* Does acute, moderate-intensity exercise (compared to gentle stretching) enhance novel word learning in healthy older adult and neurologic populations? Based on our pilot work, we hypothesize that with an optimal paradigm both recall and recognition will be significantly better in the moderate-intensity exercise condition (compared to gentle stretching).

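### For participants with aphasia the SAP specifies no exercise-versus-stretching contrast, no measure of uncertainty and no reference point for gain, so it cannot support an inferential answer to Research Question 1 in that group

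*SAP*

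**What the plan says.** Research Question 1 (Protocol, Objectives/Hypothesis/Research Questions) asks: "Does acute, moderate-intensity exercise (compared to gentle stretching) enhance novel word learning in healthy older adult and neurologic populations"? The hypothesis after it predicts a significant advantage of exercise over stretching on both recall and recognition. It names no population of its own.

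The Abstract (Methods) describes the design this way: "We will compare word learning in up to four conditions using a within-subjects crossover design". Section 6 gives one purpose of the crossover as comparing "the additive effect of moderate-intensity exercise vs. stretching on novel word learning". The timeline in section 7 shows a test before and after training on Monday, Wednesday and Friday of a block, then a single test on the Friday of the following week. Sections 6 and 8 set a ceiling of 50 for MCI and aphasia together, without a split.

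The SAP treats the two cohorts differently. Healthy adults get mixed-effects repeated-measures ANOVAs for recall, for BDNF and, post hoc, for recognition. For participants with aphasia the primary entry is "We will calculate gains for word recall at three time points": acquisition, consolidation and one-week recall. The secondary entry is mean BDNF at four sampling times. The post-hoc entry is gain scores at the same three time points, with no outcome named. The Protocol has no statistical section that adds to this.

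**The concern.** The Protocol puts a comparative question to a group that includes people with aphasia, but the SAP's plan for them contains no comparison. In that part of the SAP, exercise and stretching are mentioned only to fix when a measurement is taken. No difference between conditions is named as the quantity to estimate, and nothing expresses its uncertainty.

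The word *gain* adds a second gap. With two tests on each training day, a gain can be measured from more than one earlier test, and the choice changes what the number means. Aphasia is in the study title. Any statement about exercise in this group would rest on a quantity whose reference point was not fixed in advance, and on condition differences shown without an interval.

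**Working it through.** The documents give no effect size, SD, alpha, power or aphasia sample size, so there is no stated figure to reproduce. The check is a comparison of texts, followed by an illustration.

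**1. What each cohort's plan specifies**

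| Element | Healthy adults | Aphasia |
|---|---|---|
| Recall | Mixed-effects ANOVA | Gains |
| BDNF | Mixed-effects ANOVA | Means |
| Post-hoc outcome | Recognition | Not named |
| Inferential method | Yes | None |
| Interval, SD or SE | Not named | Not named |
| Condition term or contrast | Not named | Not named |

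The distinguishing gap is the missing inferential method. The missing condition term is common to both cohorts.

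**2. What a consolidation gain could mean**

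Write M1, M2 for Monday's first and last test, and W1 for Wednesday's first test. Take W1 as the first consolidation measure; this is my reading for a block with exercise or stretching before learning.

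- From the previous session's last test: W1 − M2. This is retention and may be negative.
- From the first test of the block: W1 − M1. This is learning.
- The two differ by (W1 − M1) − (W1 − M2) = M2 − M1, which is all of Monday's acquisition.

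If exercise raised Monday's acquisition and the benefit were fully kept to Wednesday, the second definition would show an exercise effect and the first would show none. The acquisition measure is less ambiguous: on Monday the first test of the day is also the first test of the block.

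**3. Precision of the contrast the crossover allows**

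Let n be the participants with aphasia who complete both an exercise and a stretching block. It is assumed, because the split of the ceiling of 50 is not given; n = 50 would require every place to go to aphasia. The 95% half-width of the mean paired difference, in SD of that difference, is t(0.975, n − 1)/√n:

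- n = 6: 2.571/2.449 = 1.05
- n = 8: 2.365/2.828 = 0.84
- n = 25: 2.064/5 = 0.41
- n = 50: 2.010/7.071 = 0.28

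**4. Cost of allowing for condition order**

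With a period term the half-width is t(0.975, n − 2) × √((1/n1 + 1/n2)/4), in within-sequence SD of the difference, where n1 and n2 are the numbers in each order. At n = 8:

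- Orders 4:4: 2.447 × √(0.5/4) = 0.87
- Orders 6:2: 2.447 × √(0.667/4) = 1.00

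The splits are illustrative. The Protocol says only that the order is random.

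**The case against.** The strongest reply is that a descriptive analysis was intended. The SAP uses modelling language for healthy adults and plain calculation for aphasia, which looks deliberate, and description is legitimate for a small cohort. This stands in part. But the SAP does not label the analysis descriptive, and Research Question 1 is not narrowed to match. A descriptive report also still needs a defined gain and a named outcome.

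A reader might infer that no effect size at all would be available in aphasia. The documents do not support that. An undefined gain could itself have been meant as exercise minus stretching, or gains could be tabulated by condition and subtracted. What can be said is that no contrast is specified and that precision is absent on any reading.

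A reader might also infer that the contrast is missing only for aphasia. It is not: the healthy-adult entries name no condition term either. The Protocol's intention to compare conditions should be credited to both cohorts. It still supplies no interval for aphasia.

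Two points narrow the gap further. The parallel healthy-adult entry suggests that recognition is the intended post-hoc outcome. And because the words are newly invented, recall at the first test of a block is probably near zero, so a gain from that test would be close to the raw score. That is an inference, and it does not settle the consolidation reference.

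Finally, random order might suggest a bias from order imbalance. The documents do not describe the allocation and do not exclude balanced orders, so no such bias can be claimed.

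**Conclusion.** The point holds in this form. For aphasia, the SAP specifies no exercise-versus-stretching contrast, no measure of uncertainty and no reference point for gain, and it leaves the post-hoc outcome unnamed. Followed as written, it cannot support an inferential answer to Research Question 1 in that group. The open reference point matters most for consolidation, where the same label could cover retention or learning.

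The documents give no figure that sizes the consequence. The half-widths of 0.28 to 1.05 SD rest on assumed numbers from 50 down to 6. They show only that uncertainty is large enough to need reporting across that range. The collected data remain usable and the healthy-adult analysis is unaffected, so this should be fixed but does not undermine the trial.

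**What to change.** Preferred: at each of the SAP's time points, report the mean within-participant exercise-minus-stretching difference in recall and in recognition with a 95% confidence interval. Where more than one timing was run, pair conditions of the same timing. For BDNF, report the difference between conditions in change from the pre-session sample, again with a 95% confidence interval. State the earlier test from which each gain is measured, and name recognition as the post-hoc outcome if that is intended. Allow for condition order in a sensitivity check where numbers permit.

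Alternative: label the aphasia analysis descriptive, still define gain and name the post-hoc outcome, and limit the inferential claim on Research Question 1 to healthy adults.

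The cost is SAP wording and, for the preferred route, a few lines of code. No new data are needed. The downside is wide intervals in a small cohort, slightly wider again with a period term. BDNF pairs may be fewer still, because blood is drawn from only some subjects.
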